5.2.3 Electronic diary

From the beginning of the T1DM therapy optimisation period (Visit 2) until the end of the Follow-up period (Visit 12), all patients will be provided with an electronic (e)-diary for daily use during these periods of the study. Prior to its first use, instructions on the proper use of the e-diary will be provided by the site staff. Refresher training should be provided at subsequent timepoints as deemed appropriate by the Investigator or designated site-personnel.

Daily entries into the e-diary will include at least:

- glucose values from SBGM (see Section 5.3.2.1)
- any hypoglycaemic events that have occurred
 - o for criteria for hypoglycaemic events, see Section 5.3.5.2
- insulin requirement

Any ketone measurements performed should also be entered into the e-diary if and when any data becomes available (see Section 5.3.2.2).

During the T1DM therapy optimisation period, and daily for 5 days following clinic Visit 6, data from the e-diary should be reviewed remotely by designated site personnel, paying particular attention to adjustments in the insulin regimen, glucose values, and if available, ketone measurements. In addition, the patient should be contacted by telephone (e.g. weekly during the T1DM therapy optimisation period) if e-diary data, including glucose data, is not available and/or if the data suggest closer monitoring of the patient is required. Additional clinic visits can also be arranged if necessary (for further details see Section 6.2.2); assessments at such visits would be defined according to Investigator judgement.

Throughout the trial, the Investigator and/or designated site personnel should review the patient's glucose and e-diary results to determine if treatment adjustments need to be implemented. As a minimum, this review must take place at the timepoints indicated in the Flow Chart.

The e-diary data will be transferred to a vendor server for data collection and transfer to the Sponsor.

Proprietary confidential information © 2016 Boehringer Ingelheim International GmbH or one or more of its affiliated companies

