6.7 BASELINE, TIME WINDOW, AND CALCULATED VISITS

With regard to efficacy and safety endpoints, the term "baseline" refers to the last observed measurement prior to administration of any randomised study medication. For specific endpoints, baseline definitions are as follows:

Serum beta-hydroxybutyrate (BHB)

- Serum BHB sampled at the site and analysed at the central laboratory

Baseline will be defined as the fasted measurement observed at Visit 6, before first drug intake.

- Capillary patient self-measured BHB via the ketone meter and reported in the diary

For the analysis on morning or daily measurements (see [Section 7.8.2.5](#)), baseline will be defined as the mean of morning or daily measurements reported during the run-in period, respectively (Visit 5 to Visit 6, including the day of first administration of trial drug).

[REDACTED]

Hypoglycaemia rate

The event rate of hypoglycaemia (using the respective endpoint definition) during the 4 weeks prior to randomisation (from Day -28 up to Day -1). Collapsing will be performed as per the rules in Sections [5.4.6.3](#) and [5.4.7](#). Rates will be presented per 30 days and also per patient year.

Insulin dose (total daily, total daily basal or total daily bolus)

Mean daily insulin requirement during the run-in period (Visit 5 to Visit 6, excluding day of randomisation). If < 4 days of valid insulin data is reported during the run-in period then the measurement will be considered missing. For data handling rules see [Section 5.4.6.2](#).

[REDACTED]

[REDACTED]

[REDACTED]

[REDACTED]

[REDACTED]

Table 6.7: 1 Endpoint specific follow-up period for the assignment to active treatment

Endpoint	Last day of assignment to treatment phase (days after study drug stop date)
Efficacy	
HbA _{1c}	7
FPG	1
MDG	1
CGM	*
Body weight	1
Blood pressure	1
Waist circumference	7
Insulin dose	0
Hypoglycaemia	1
UACR	1
Health economics and QoL	1
Safety	
Adverse events	7
Hypoglycaemia ^[1]	1
Hepatic injury ^[2]	30
Safety laboratory measurements	3
AST/ALT/TBL ^[3]	30
Pulse rate	1

*Refer to [Section 5.4.4](#) for the assignment of CGM measurements to the on-treatment period

[1] Refer to all hypoglycaemia analyses except the general hypoglycaemia AE analysis by SOC and PT.

[2] Refer to a sensitivity analysis including all hepatic injuries with an onset date up to 30 days after the study treatment stop (see Section 7.8.1.4).

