7.5 SECONDARY ENDPOINTS

7.5.1 Key secondary endpoints

7.5.1.1 Rate of symptomatic hypoglycaemic AEs with confirmed plasma glucose <54 mg/dL and/or severe hypoglycaemic events confirmed by adjudication

[figure not shown]
Confirmatory analysis

The analysis of the rate of symptomatic hypoglycaemic AEs with confirmed plasma glucose <54 mg/dL and/or severe hypoglycaemic events confirmed by adjudication will utilise a negative binomial model, with terms for treatment, continuous baseline rate, continuous baseline HbA1c, continuous baseline eGFR and pre-existing insulin therapy as fixed effects and log(time at risk) as an offset. The results will be presented as a rate per patient-year. This analysis will be performed on the FAS (OC).

The baseline rate of symptomatic hypoglycaemic AEs with confirmed plasma glucose < 54 mg/dL and/or severe hypoglycaemic events confirmed by adjudication will be calculated based on the event rate during the 4 weeks prior to randomisation, see [Section 6.7](#).

The analysis of the rate from Week 5 to Week 26 will include all on-treatment events from the start of Week 5 (Day 29) until one day after treatment stop date. This period will also define the time at risk.

The analysis of the rate from Week 1 to Week 26 will include all on-treatment events from the date of first study drug intake until one day after treatment stop date. This period will also define the time at risk.

[REDACTED]

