The Kaplan-Meier graph will present data up to the end of the treatment period.

Patient without an event will be considered censored at the date of the last trial drug intake plus one day.

A log-rank test will be computed to test the equality of the survival curves.

Patients with CEC confirmed severe hypoglycaemia will be tabulated by treatment and characteristics of hypoglycaemia including minimum glucose level and time to onset of first episode. The frequency of severe nocturnal hypoglycaemia AE (i.e. any hypoglycaemia event with an onset from 0:00 midnight to 5:59 a.m.) will also be evaluated as part of these characteristics.

Finally, the severe hypoglycaemia considered serious or requiring third person assistance will be tabulated using the narrow SMQ Hypoglycaemia. This analysis will be restricted to patients with CEC confirmed severe hypoglycaemia.

- Analysis of frequency of hypoglycaemia adverse events

The number of CEC confirmed severe hypoglycaemic episodes will be first tabulated by treatment and characteristics of hypoglycaemia. When appropriate, the number of episodes per patient-year will be provided in this analysis. The time at risk for severe hypoglycaemia [patient-years] will be derived similarly as for ketoacidosis, but in using 1 day of washout instead of 7 days in the calculation.

A negative binomial model will be fitted to analyse the event rate of CEC confirmed severe hypoglycaemia per patient-years, with terms for treatment, continuous baseline rate, continuous baseline HbA1c, continuous baseline eGFR (CKD-EPI, creatinine) and pre-existing insulin therapy as fixed effects and log(time at risk) as an offset.

In addition, the severe hypoglycaemic episodes that have been confirmed by the adjudication committee will be represented on a graph by hour of the day (from midnight to 11:59 pm).

- Investigator defined AESI severe hypoglycaemia adverse event endpoint

Patients with investigator defined AESI severe hypoglycaemia will also be summarised by treatment and event characteristics, as well as the investigator defined AESI severe hypoglycaemic episodes.

Patients with investigator defined AESI severe hypoglycaemia will additionally be summarised by SOC, PT and treatment group.

Lower limb amputation

A frequency table summarising the investigator defined AESI lower limb amputation events will be created by SOC and PT. The table will be then repeated for serious events, and for events leading to treatment discontinuation.

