7.8.1.5 Other specific adverse events

Hypoglycaemia

- Hypoglycaemia adverse events

In this sub-section, only hypoglycaemia reported by the investigator as adverse events will be discussed. For specifications on analyses on severe hypoglycaemia adverse event, refer to [Section 7.8.1.4](#).

Refer to [Section 9.3](#) for details on the derivation of the hypoglycaemia adverse event endpoints listed below.

Every episode of $PG \leq 70$ mg/dL should be documented with the respective time and date of occurrence. This includes hypoglycaemia with glucose values < 54 mg/dL and all symptomatic and all severe hypoglycaemic events. On the basis of this information the hypoglycaemic adverse event will be classified according to the following protocol defined categories:

- Asymptomatic hypoglycaemia with $PG \leq 70$ mg/dL
 - Documented symptomatic hypoglycaemia with $54 \text{ mg/dL} \leq PG \leq 70 \text{ mg/dL}$ and typical symptoms
 - Documented symptomatic hypoglycaemia with $PG < 54 \text{ mg/dL}$ and typical symptoms and no need for external assistance
 - Severe hypoglycaemia, events requiring assistance
- Analysis of number of patients with hypoglycaemia adverse events

The frequency of patients with protocol defined hypoglycaemia adverse event will be presented by treatment.

The frequency of patients with hypoglycaemia adverse event according to investigator's judgment will be tabulated by treatment, SOC and preferred term.

- Analysis of frequency of hypoglycaemic adverse events

Similarly as for the analysis on patient level, a summary on the number of protocol defined hypoglycaemia adverse event episodes will be produced per patient-years.

Then, descriptive statistics will be produced for the predefined protocol further safety endpoint “rate of symptomatic hypoglycemic AE with confirmed $PG < 54$ mg/dL and/or severe hypoglycaemic AE confirmed by the adjudication, per 30 days, from Week 1 to Week 4”. A negative binomial model with terms for treatment, baseline rate, continuous baseline HbA1c, continuous baseline eGFR (CKD-EPI, creatinine) and pre-existing insulin therapy as fixed effects and log (time at risk [30 days]) as an offset will also be prepared. These two analyses will furthermore be replicated on the FAS.

Step 1 and Step 2 of the TSAP [Section 5.4.7](#) collapsing rules will apply, in order to avoid the double-counting of episodes between adjudicated severe hypoglycaemia data and hypoglycaemia AE data.

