- Patient-reported hypoglycaemia events

The endpoints describe in this sub-section will be exclusively based on patient-reported hypoglycaemia data.

A summary presenting the number of patients with the following endpoints will be tabulated:

- Asymptomatic hypoglycaemia with $PG \leq 70$ mg/dL
- Symptomatic hypoglycaemia with $PG \leq 70$ mg/dL
- Asymptomatic hypoglycaemia with $PG < 54$ mg/dL
- Symptomatic hypoglycaemia with $PG < 54$ mg/dL
- Nocturnal symptomatic hypoglycaemia with $PG \leq 70$ mg/dL
- Nocturnal symptomatic hypoglycaemia with $PG \leq 70$ mg/dL
- Nocturnal asymptomatic hypoglycaemia with $PG < 54$ mg/dL
- Nocturnal asymptomatic hypoglycaemia with $PG < 54$ mg/dL

The number of episodes per patient-year will be analysed for these endpoints as well, for which the TSAP [Section 5.4.6.3](#) collapsing rules will apply.

A negative binomial model will be fitted to analyse the symptomatic hypoglycaemia with $PG < 54$ mg/dL, with terms for treatment, continuous baseline HbA1c, continuous baseline eGFR (CKD-EPI, creatinine) and pre-existing insulin therapy as fixed effects and log(time at risk) as an offset.

Urinary and genital infections

The following additional specific adverse events will also be assessed and be tabulated by treatment group:

- Genital tract infections (narrow BICMQ, investigator assessment)
- Urinary tract infections (UTI) (narrow BICMQ, investigator assessment)

The serious genital infection events as well as the genital infection events leading to treatment discontinuation will additionally be summarised using the narrow project defined PT list.

Similarly, the serious UTI events as well as the UTIs leading to treatment discontinuation will be summarised using the BICMQ.

A frequency table for complicated urinary tract infections/pyelonephritis/urosepsis where 'complicated urinary tract infections' are defined as serious AEs from the narrow BICMQ UTI, all events included in the sub-BICMQ pyelonephritis and all events of preferred term urosepsis will in addition be provided .

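### The patient-reported hypoglycaemia model leaves out the baseline event rate that the SAP's other hypoglycaemia rate models include and that SAP 6.7 already defines

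*SAP*

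**What the plan says.** For patient-reported events, SAP 7.8.1.5 plans episode counts ("The number of episodes per patient-year will be analysed for these endpoints as well"), using the collapsing rules of Section 5.4.6.3. It then plans a negative binomial model for symptomatic events below 54 mg/dL "with terms for treatment, continuous baseline HbA1c, continuous baseline eGFR (CKD-EPI, creatinine) and pre-existing insulin therapy as fixed effects", with log time at risk as offset. The SAP history table lists this model as an addition in the October 2017 revision.

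The other hypoglycaemia rate models read differently:

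- SAP 7.5.1.1, key secondary rate: "negative binomial model, with terms for treatment, continuous baseline rate, continuous baseline HbA1c".
- SAP 7.8.1.4, adjudicated severe events: "event rate of CEC confirmed severe hypoglycaemia per patient-years, with terms for treatment, continuous baseline rate, continuous baseline HbA1c".
- SAP 7.8.1.5, Week 1 to 4 rate: "A negative binomial model with terms for treatment, baseline rate, continuous baseline HbA1c".

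SAP 6.7 defines the baseline as "The event rate of hypoglycaemia (using the respective endpoint definition) during the 4 weeks prior to randomisation (from Day -28 up to Day -1"). It continues "Collapsing will be performed as per the rules in Sections" 5.4.6.3 and 5.4.7. Under Protocol 5.2.3, daily e-diary entries from Visit 2 include "any hypoglycaemic events that have occurred".

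**The concern.** A patient's own event rate before treatment can be expected to predict the rate afterwards, more strongly than HbA1c, eGFR or insulin modality. If so, leaving it out moves explainable between-patient variation into the dispersion parameter and widens the interval for the rate ratio. Protocol 3.2 gives capturing a true baseline hypoglycaemia rate as one purpose of the optimisation and run-in periods, so the design collects this quantity. The baseline table in SAP 7.1.1 shows only adjudicated severe and AE-based rates. In the readable text, a chance imbalance in the patient-reported baseline rate would therefore be neither adjusted for nor displayed.

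A separate, minor mismatch concerns the strata. Participation in the CGM substudy is one of four stratification factors (Protocol 7.1 and 7.6). The other three appear in the confirmatory models as covariates, but CGM participation does not (SAP 7.4.1 and 7.5.1).

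**Working it through.** **1. Term lists side by side**

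| Model | Treatment, HbA1c, eGFR, insulin therapy | Baseline rate |
|---|---|---|
| Key secondary rate (SAP 7.5.1.1, both time windows) | yes | yes |
| Adjudicated severe (SAP 7.8.1.4) | yes | yes |
| Week 1 to 4 rate (SAP 7.8.1.5) | yes | yes |
| Patient-reported, below 54 mg/dL (SAP 7.8.1.5) | yes | **no** |

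**2. Is the covariate available?** The flow chart puts Visit 2 at Day -56, so the diary covers Day -28 to Day -1. SAP 6.7 defines the rate under each endpoint's own definition and cites Section 5.4.6.3, the same collapsing rules used for the patient-reported episodes. No new data or definition is needed.

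**3. The plan's own figure.** The documents give no size or power figure for any hypoglycaemia model. The only stated calculation is for HbA1c (Protocol 7.7: difference 0.3, SD 0.9, two-sided alpha 0.025, power 90%):

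n = 2 × (2.2414 + 1.2816)² × 0.9² / 0.3² = 223.4, so 224 per arm against 225 stated. Power at 225 is 90.2%. This reproduces, and it supplies the 225 per arm used below.

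**4. Size of the precision loss.** All event rates, dispersions and drift values are assumed.

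- Set-up: gamma-Poisson counts, 225 per arm, 26 weeks, rate ratio 0.85. Rates were 3, 5, 10, 15, 20 and 30 per patient-year, gamma shape 0.6 or 1.0, and lognormal drift SD between baseline and treatment 0.4 or 0.8. That is 6 × 2 × 2 = 24 scenarios with 120 replicates each.
- Each data set was fitted by maximum-likelihood negative binomial regression with and without the 28-day baseline rate as a linear term.

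| Scenario | SE without | SE with | (SE without / SE with)² |
|---|---|---|---|
| Smallest gain (3/yr, shape 1.0, drift 0.8) | 0.1539 | 0.1497 | 1.06 |
| Largest gain (30/yr, shape 0.6, drift 0.4) | 0.1295 | 0.0988 | 1.72 |

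The SE reduction was 3–6% at 3 per year, 8–15% at 10 and 14–24% at 30. At 10 per year, shape 0.6 and drift 0.4 (the favourable end for that rate), the SE falls from 0.136 to 0.115. The ratio of upper to lower 95% limit then goes from exp(2 × 1.96 × 0.136) = 1.70 to exp(2 × 1.96 × 0.115) = 1.57. The empirical SD of the estimates also fell in 23 of the 24 scenarios.

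A second simulation used different assumptions: rate ratio 0.8, rates 5, 15 and 30 per year, gamma dispersion 0.5, 1 and 2, and 80 trials per setting. The variance with the term relative to without ran from 0.945 to 0.591, a cut of about 5% to 41%. Mean log rate ratios showed no systematic shift from the true -0.223 in either model.

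**5. CGM participation (minor).** Protocol 3.1 expects about 30% participation. For an assumed HbA1c difference d between participants and non-participants, R² = 0.3 × 0.7 × d² / 0.81 and k = √(1 − R²). The standardised effect is 0.3 / (0.9 × √(2/225)) = 3.5355.

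| d | R² | SE too wide by (1/k − 1) | True level 2(1 − Φ(2.2414/k)) | Power without the term | Power with it |
|---|---|---|---|---|---|
| 0.1 | 0.0026 | 0.1% | 0.0248 | 90.25% | 90.30% |
| 0.3 | 0.0233 | 1.2% | 0.0233 | 90.48% | 90.92% |

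Power without the term is Φ((3.5355 − 2.2414)/k). With it, power is Φ(3.5355/k − 2.2414).

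**The case against.** The strongest reply is that this is a modelling preference in a supportive safety analysis. Protocol 7.3.4 calls the safety analyses mostly descriptive and plans no hypothesis tests, and treatment is randomised, so the rate ratio is not biased. That stands, and it sets the low weight of the point.

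It can also be said that matching the covariate lists does not make the analyses comparable. The event source differs (diary, investigator-reported AEs, adjudicated events), and the key secondary model uses the FAS while this one uses the treated set. No readable passage says the patient-reported model is meant to support the AE-based rates. This is fair, so comparability is only a weak reason for the change. The case rests on precision.

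Sections 5.4.6.3, 5.4.7 and 9.3, and parts of the change history, are not readable. A reason for the omission, or a baseline-adjusted version of the model, could sit there. The mismatch in the term lists is certain. The absence of a reason is established only for the readable text.

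The size of the gain depends on assumed inputs and varies about eight-fold. The simulations had no missing diary days. SAP 7.5.1.3 notes that the diary source for insulin dose is not cleaned. If the same holds for diary events, the baseline rate would be noisier and the gain smaller. The range should be read with that in mind.

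On CGM, the SAP follows the models fixed in Protocol 7.3.1.1 and 7.3.2.1, the documents do not show that participation is prognostic, and redacted analyses may cover it. That is why it is optional.

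**Conclusion.** The omission is real as written. All three comparable specifications contain a baseline rate and this one does not, although the rate is defined and the data are collected. The consequence is a wider interval than necessary, with the SE higher by an amount that adjustment would cut by roughly 3% to 24% under the assumed rates, dispersions and drift. There is no systematic bias, no change to any figure in the documents, and no effect on the key secondary tests or the alpha scheme. The point is worth making because the improvement is almost free.

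The CGM point is smaller still. The tests are at most slightly conservative (true level 0.0248 to 0.0233 against 0.025 for an assumed 0.1 to 0.3% HbA1c difference), and unaffected if participation is not prognostic.

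**What to change.** In SAP 7.8.1.5, add a continuous baseline rate to the patient-reported negative binomial model: patient-reported symptomatic hypoglycaemia with plasma glucose below 54 mg/dL, Day -28 to Day -1, derived as in SAP 6.7. Its terms then match the other three models. If the omission is deliberate, one sentence giving the reason is enough. The cost is one covariate from data already collected, in a non-confirmatory model.

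Optionally, add CGM participation (yes/no) as a fixed effect in the SAP 7.4.1 and 7.5.1 models so that the analysis matches the stratified randomisation. This costs one degree of freedom per model. Because it departs from the models in the protocol, it must be declared in SAP Section 4 before unblinding.

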7.8.1.6 Events qualifying for external adjudication by the Clinical Event Committee (CEC)

Independent external CECs regularly review cardiovascular, neurovascular, hepatic, severe hypoglycaemia, and ketoacidosis events and evaluate whether pre-specified criteria for these adjudication endpoints are met. Details on composition of the CECs, responsibilities and clinical event definitions are provided in separate CEC charters. Events qualifying for adjudication will be selected based on the latest CEC charter versions.

The CECs will be provided with additional, specified background material on the patients with these events and perform an assessment of the events. Adjudication assessments will be incorporated to the database.

Refer to [Section 7.8.1.4](#) for details on analyses for severe hypoglycaemia and ketoacidosis events confirmed by adjudication.

Frequency table by treatment group will be provided for the adjudicated cardiovascular and neurological endpoints and for the preferred terms in the specified SMQs of events. Table will also be provided for events that were confirmed or non-assessable.

The cardiovascular and neurovascular events qualifying for adjudication will be selected based on the following SMQs:

- Ischemic heart disease, excluding PTs “Blood creatine phosphokinase abnormal” and “Blood creatine phosphokinase increased”
- Cardiac failure, excluding PTs “Oedema”, “Oedema peripheral” and “Peripheral swelling” unless there are reported as serious events
- Torsade de pointes / QT prolongation
- Cerebrovascular disorders, excluding PT “Fahr's disease”

- Further simple preferred terms
- All fatal cases

7.8.1.7 AEs while patients taking wrong medication

A listing will be provided for AEs that occurred while a patient was taking the wrong medication.

7.8.2 Laboratory data

For continuous safety laboratory parameters standardised and normalised values will be derived as well as the differences to baseline. The process of standardisation and normalisation as well as standard analyses for safety laboratory data are described in the BI guidance for the Display and Analysis of Laboratory Data (10). All analyses considering multiple of times upper limit of normal (ULN) will be based on original and not normalized data.

The analyses of laboratory data will be descriptive in nature and will be based on BI standards.

Results of laboratory analyses will be presented based on both SI units and US conventional units.

Baseline for safety laboratory parameters will be the last available measurement before the start of randomised study drug. In general, laboratory measurements taken up to 3 days after the last administration of randomised study drug will be considered as on-treatment. The exception will be for the liver enzyme elevation analysis (see below).

Only patients with at least one available on-treatment value will be included in the analysis of an individual laboratory parameter. All individual data will be presented in listings.

